**Open Label Phase-II Randomized Trial of 3 Regimens of
Liposomal Amphotericin B as Induction Therapy for
Disseminated Histoplasmosis in AIDS patients**

STUDY PROTOCOL

CLINICAL TRIALS REGISTRATION NCT04059770

February 24, 2021

STUDY CONCEPT

Background

Histoplasma capsulatum is the etiologic agent of histoplasmosis, a systemic mycosis that is highly endemic in the Americas and also being identified in other parts of the globe [1, 2]. Histoplasmosis may disseminate in immunosuppressed patients, particularly those infected by the HIV. Accordingly, histoplasmosis has been an AIDS-defining infection since 1987 [3]. Disseminated histoplasmosis (DH) is one of the main AIDS-defining infections and a major killer of HIV-infected patients in South and Central America [3-5].

Most AIDS patients with histoplasmosis require high dose of antifungal agents. Even though liposomal amphotericin B (L-AmB) is considered the drug of choice for histoplasmosis in AIDS, as agreed in the Infectious Diseases Society of America guidelines [6], and supported by a randomized clinical trial [7], many patients in Latin America are still treated with high doses of deoxycholate amphotericin B (d-AmB) for periods as long as 2-6 weeks. These regimens are associated with considerable toxicity, and therefore reduced efficacy. Overall mortality in patients using d-AmB in Latin America, where *Histoplasma* antigen detection is rarely available, can be as high as 50% [5]. A better treatment strategy is ultimately needed.

L-AmB has several advantages over d-AmB in the treatment of DH: lower infusion-related toxicity [8], and reduced hematological and renal toxicity [9, 10]. In addition, L-AmB has long half-life and effectively penetrates in tissues such as liver, spleen and the central nervous system [11]. Considering that the antifungal effect of the polyenes depends on peak concentrations, treating patients with a high dose of L-AmB for short periods [instead of standard doses for longer periods] is a promising approach. Such strategy has successfully been studied in antifungal prophylaxis [12, 13], febrile neutropenia [14], leishmaniasis [15], and more recently, cryptococcosis [16]. When used for antifungal prophylaxis in hematology patients, doses of up to 15 mg/kg of L-AmB were given without significant toxicities [17]. Conversely, toxicity has been linked to repeated administrations of L-AmB [12]. Despite

these encouraging data, the strategy of using single high dose of L-AmB has never been tried in histoplasmosis.

Research Justification

DH is an endemic disease that frequently occurs in institutions with no access to modern diagnostic tests and that have limited availability of L-AmB. If a strategy of less frequent, high doses of L-AmB shows activity in DH, this will allow for reducing the cost of treatment in developing countries, in addition to improving safety and tolerability. Based on what has been published so far, safety does not seem to be a concern with high single doses of L-AmB. Results of this study may serve as a basis for a future phase III randomized comparative trial.

Objectives

To determine and compare the activity and safety of three regimens of L-AmB, as induction therapy of DH in AIDS patients, as well as to determine the safety of the three regimens.

Methods

Trial design

This will be a prospective randomized non-comparative multicenter open label trial of induction therapy for DH in AIDS, followed by oral therapy with itraconazole.

The total sample size planned is 99 patients (33 patients per study arm). This sample size considers 10% of dropout.

The study will be conducted in compliance with the declaration of Helsinki, as well as ICH GCP guidelines. Participation in the study will require written consent. The study will be registered at www.clinicaltrials.gov, before trial initiation and patient recruitment.

Participants

We will include adult (≥ 18 years old) patients infected with the HIV (AIDS) who are diagnosed with DH, by the means of either (i) positive *Histoplasma* antigen in the urine (IMMY monoclonal antibody test); (ii)

confirmation by classical methods (microscopy, culture, or histopathology); or (iii) positive *Histoplasma* qualitative PCR (performed in accordance to [18]) in BAL samples, as well as bone marrow aspirates and tissue samples. Patients who are both antiretroviral treatment (ART) naïve and ART exposed will be recruited.

Exclusion criteria

Patients with previous diagnosis of histoplasmosis will not be considered for this study. We will also exclude pregnant or lactating woman, patients with renal failure (serum creatinine and urea >1.5 times the upper limit of normality), abnormal aminotransferases (up to >3 times the upper limit of normality), and patients with a previous serious reaction to a polyene antifungal drug. Patients who received more than one dose of a polyene antifungal drug in the last 48 hours will be excluded, as well as patients who refuse content to participate in the study. Patients diagnosed with histoplasmosis affecting the central nervous system will not be allowed to participate in the study. In addition, patients who are expected to die within 48 hours of enrolment will also be excluded, based on the judgment made by the attending physician. Patients diagnosed with tuberculosis will be excluded; as well those receiving drugs that cause significant drug-drug interaction (relative or absolute) with itraconazole.

Study settings

Six medical centers in Brazil, will recruit patients for this study: Santa Casa de Misericórdia de Porto Alegre, Hospital de Clínicas de Porto Alegre, Hospital Nossa Senhora da Conceição, Hospital de Doenças Tropicais, Hospital São Jose de Doenças Infecciosas, and Hospital Giselda Trigueiro.

Intervention

AIDS patients with DH will be randomized to one of three study arms: (i) single IV dose of L-AmB at 10 mg/kg; (ii) single IV dose of 10 mg/kg of L-AmB on day 1, followed by 5 mg/kg of L-AmB on day 3; and (iii) L-AmB at 3 mg/kg IV for 2 weeks. Induction therapy will be followed in all patients by oral therapy with itraconazole capsules at 400 mg/daily for a year.

Drug reconstitution and administration

L-AmB (AmBisome; Gilead Sciences, San Dimas, California, USA), a lyophilized liposomal preparation of amphotericin B, will be reconstituted according to the manufacturer's instruction and given intravenously at fixed doses, according to the randomization arm. L-AmB concentration should be of 0.2 mg/ml in 5% dextrose, and the drug should be infused over 2 hours, preferably in a central line. Patients will be monitored for the occurrence of infusion-related toxicity during and after drug infusion.

Primary endpoint

Clinical and mycological successes will be the primary outcomes for this study. A successful clinical response to induction therapy will be defined according to, as a maximum daily temperature $<37.8^{\circ}\text{C}$ for 72 hours; no increase in severity of clinical signs, symptoms, or laboratory abnormalities attributable to histoplasmosis; and the resolution of at least one of the signs or symptoms of histoplasmosis that qualified the patient for study enrollment [7].

Primary study outcome will be determined at day 14 of the study.

Secondary endpoints

Overall mortality and investigator-attributable mortality due to histoplasmosis will be determined at day 14 of study. Overall Survival (OS) will also be determined at 12, 24, and 48 weeks of study. OS will be considered as the time from randomization until death from any cause.

Secondary endpoint will also include need for an additional antifungal course with L-AmB, during 24 weeks of follow up.

Median percentage of change in renal and hepatic function at 14 days will be compared with baseline values.

Frequency of infusion-related toxicity with L-AmB will be recorded.

Clearance of blood cultures will not be used as a criterion for mycological response in this study, due to the limited sensitivity of blood culture in histoplasmosis [19]. Fungal clearance will also not be used as a criterion for mycological response. Differently from cryptococcosis, in which fungal burden is easily obtained and quantified in cerebrospinal fluid samples,

in histoplasmosis commonly a single positive sample is obtained along patient investigation (e.g., microscopy, culture, and/or histopathology).

Non-culture laboratory markers have proved to be useful adjuncts in monitoring the response to systemic histoplasmosis [20, 21]. In this study, we will evaluate the effect of a decrease of at least 50% in *Histoplasma* urinary antigen concentrations [19] along the first 2 weeks of therapy as a secondary endpoint, and the association of such reductions with clinical response to antifungal therapy.

Rescue therapy

The study protocol will allow patients to receive additional courses of L-AmB (at 3 mg/kg daily) in case the attendant physician suspect of absence of response with the induction regimen. This will apply for failing patients receiving a single 10 mg/kg of L-AmB; or 10 mg/kg on day 1, followed by 5 mg/kg on day 3. In these cases, L-AmB should be given up to a maximum period of 2 weeks. The estimated frequency of L-AmB as rescue therapy will be based on the frequency of failure with L-AmB at 3 mg/kg in patients with DH and AIDS (i.e., 12%) [7]. Considering that 66 patients will be evaluated in arms (i) and (ii) of the study (high-doses of L-AmB), in a pessimistic scenario we aim to provide 8 additional treatments with L-AmB.

Time for initiating ART

Physicians will be instructed to initiate ART as soon as possible in AIDS patients with DH, since immune reconstitution syndrome is uncommon in patients with DH [22]. In Brazil, initial ART consists of dolutegravir, lamivudine, and tenofovir. History of previous antifungal use and known resistance patterns will also be considered in the decisions about ART.

Statistical analyses

Descriptive statistics will be used to summarize the data. Mean, standard deviation, median, interquartile range and minimum and maximum will be described for continuous variables. Categorical variables will be summarized by absolute and relative frequencies. Kaplan-Meier method will be used in order to describe OS. Despite the non-comparative status of the

trial, exploratory comparisons will be performed across subgroups. Continuous variables will be compared using two sample t-test, paired sample t-test, Mann-Whitney test, Wilcoxon signed-rank test, one-way ANOVA or Kruskal-Wallis test, as appropriate and necessary. Categorical variables will be compared with Fisher exact test or chi-square test, as appropriate. All p-values will be two-sided.

We expect that the three arms will have the same clinical response. For each arm, when the sample size is 29, a two-sided 90% confidence interval will extend 10% from the observed proportion for an expected proportion of response equal to 88% [as extracted from the Johnson trial]. Considering a dropout of 10%, the sample size per arm will be 33. The total sample size for the study will be 99 patients. Data analysis will be performed using SPSS software.

Ethical aspects

Conduction of this study is conditioned to ethical approval by local IRBs. Since this trial will not aim to modify any regulatory aspect related to L-AmB in Brazil, ANVISA (Brazilian Health Regulatory Agency) will not be consulted. The study will also be registered at clinicaltrials.gov.

Study activities

Clinical evaluations will take place at baseline, day 3, day 7, and day 14 (End of Study Visit). End of follow up will occur at week 48, and mortality will be determined at weeks 12, 24, and 48.

The study will recommend careful attention to hydration status, and close monitoring of renal function, hepatic function, and electrolytes. Unless clinically advisable, physicians are requested to give one liter of saline 0.9% solution intravenously before L-AmB infusion. Patients should also be on prophylaxis with daily trimethoprim-sulfamethoxazole.

Table 1 shows the procedures predicted for this study. Clinical and laboratory adverse events will be graded using the NIH DAIDS Toxicity Table [23]. Itraconazole therapeutic drug monitoring will be offered to sites at day 7 and day 14 of study. The attending physicians will use this information according to their personal judgment.

Table 1. Study activities.

	Baseline	Day 3	Day 7	Day 14	Week 12	Week 24	Week 48
Informed Consent	X						
History	X						
Physical Exam	X		X	X			
Maximum Temp	X	X	X	X			
Glasgow coma scale	X		X	X			
Chemistry (including magnesium) and blood counts	X		X	X			
HIV documentation	X						
CD4 count determination							
Pregnancy Test	X						
Chest X-ray	X			X			
Study Drug accountability	X						
Concomitant medications	X	X	X	X			
Adverse Events		X	X	X			
Survival determination				X	X	X	X
Molecular test for TB	X						
Urine for Histo antigen test	X		X	X			
Histoplasma PCR (as needed)	X						
Fungal culture (as needed)	X						
Microscopy (as needed)	X						
Histopathology (as needed)	X						
Itraconazole TDM			X	X			
Lysis centrifugation (if available)	X						
Study responde determination				X			
Need for additioal course of L-AmB				X	X		

Study Plan Schedule Strategy

Table 2 shows the predicted timeline for this study.

Table 2. Study plan.

References

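### One dilution and one infusion time for all doses: followed as written, 10 mg/kg becomes 50 ml/kg of 5% dextrose in 2 hours

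*Combined protocol and SAP*

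**What the plan says.** The Intervention section lists three regimens. Arm (i) is "i) single IV dose of L-AmB at 10 mg/kg". Arm (ii) has the same first dose and adds 5 mg/kg on day 3. Arm (iii) is "iii) L-AmB at 3 mg/kg IV for 2 weeks".

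The section on drug reconstitution and administration then gives one rule for all of them: "L-AmB concentration should be of 0.2 mg/ml in 5% dextrose, and the drug should be infused over 2 hours". The sentence before it cites the manufacturer's directions, but for reconstituting the product. The final concentration and the infusion time are set by the protocol itself.

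Several provisions bear on fluid and safety:

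- The same section says: "Patients will be monitored for the occurrence of infusion-related toxicity during and after drug infusion".
- Study activities says: "The study will recommend careful attention to hydration status, and close monitoring of renal function, hepatic function, and electrolytes". It also asks physicians to give a litre of 0.9% saline before L-AmB. The exception attached to that request seems to be worded in reverse; I read it as leaving the physician free to omit the saline.
- Exclusion criteria removes "patients with renal failure (serum creatinine and urea >1.5 times the upper limit of normality", as the protocol defines it.
- Study activities schedules a clinical evaluation on day 3, and Table 1 marks adverse events, temperature and concomitant medication for that visit. The Table 1 row "Chemistry (including magnesium) and blood counts" is marked at baseline, day 7 and day 14.

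**The concern.** When concentration and duration are both fixed, volume and rate rise in direct proportion to dose. A dilution that gives a modest volume at 3 mg/kg gives a much larger one at 10 mg/kg, and the protocol does not separate the two. A pharmacy that follows the text exactly would prepare a very large bag of 5% dextrose for each high-dose patient, to run in over 2 hours. These patients have AIDS and disseminated disease, and may have had saline just before.

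What is at stake is patient safety in the two experimental arms. The issue is an operative instruction that was not adapted to the dose. It is not a disagreement between two figures that the protocol states.

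**Working it through.** The plan states no infusion volume or rate, so there is no figure of its own to reproduce.

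**Inputs from the protocol**

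- Doses: 10, 5 and 3 mg/kg (Intervention).
- Final concentration: 0.2 mg/ml in 5% dextrose, all doses (Drug reconstitution and administration).
- Infusion time: 2 hours, all doses (same section).
- Pre-infusion saline: 1 litre, if given (Study activities).
- Planned patients in arms (i) and (ii): 2 × 33 = 66, the figure that Rescue therapy also uses.

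**Input that the protocol does not give**

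- Body weight: assumed 60 kg, range 40 to 80 kg.

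**Step 1: volume and rate per kilogram (no assumption needed)**

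Volume (ml/kg) = dose (mg/kg) / 0.2 mg/ml. Rate (ml/kg/h) = volume / 2 h.

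| Dose | Volume | Rate |
|---|---|---|
| 10 mg/kg | 10/0.2 = 50 ml/kg | 50/2 = 25 ml/kg/h |
| 5 mg/kg | 5/0.2 = 25 ml/kg | 25/2 = 12.5 ml/kg/h |
| 3 mg/kg | 3/0.2 = 15 ml/kg | 15/2 = 7.5 ml/kg/h |

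The 10 mg/kg infusion is 50/15 = 3.3 times the 3 mg/kg infusion in both volume and rate, which is simply the ratio of the doses.

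**Step 2: litres per infusion at the assumed weights**

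| Dose | 40 kg | 60 kg | 80 kg |
|---|---|---|---|
| 10 mg/kg | 2.0 L | 3.0 L | 4.0 L |
| 5 mg/kg | 1.0 L | 1.5 L | 2.0 L |
| 3 mg/kg | 0.6 L | 0.9 L | 1.2 L |

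If the litre of saline is given first, the fluid around a 10 mg/kg dose is 2.0 + 1 = 3.0 L, 3.0 + 1 = 4.0 L and 4.0 + 1 = 5.0 L at these weights.

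**Step 3: does any other text change these figures?**

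- Following the manufacturer for reconstitution does not alter the final concentration, which the next sentence fixes.
- Watching for infusion reactions, attending to hydration and monitoring electrolytes may detect a problem or prompt a physician to act. None of them sets a volume, a rate or a different dilution.
- Excluding renal failure removes some vulnerable patients but leaves the infusion unchanged for those enrolled.
- The day 3 evaluation comes after the first infusion. The first scheduled chemistry after that infusion is on day 7, although sites may test sooner under the general monitoring advice.

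No dose-specific dilution, volume ceiling or rate ceiling appears anywhere in the document.

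**The case against.** The strongest objection is that harm is not shown. The documents give no tolerable volume or rate, and whether 50 ml/kg in 2 hours is unsafe, or departs from the product instructions, cannot be settled from them. That stands, and it limits the conclusion to the volumes and the need to correct or confirm the instruction.

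Other parts of the opposing case have some force:

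- Dose, concentration and time together do fix a volume and rate for each patient, so the protocol is not silent. The question is whether the fixed value was intended for 10 mg/kg.
- Pharmacies will have the product instructions to hand for reconstitution, so a mismatch may be noticed. This makes an error less likely, but it relies on sites departing from the written protocol.
- The value 0.2 mg/ml may be the low end of an intended range. The text gives no range.
- If arm (iii) is dosed daily for 14 days, its total is 14 × 15 = 210 ml/kg, more than the 50 ml/kg of arm (i) or the 50 + 25 = 75 ml/kg of arm (ii). That total is spread over two weeks. For acute load, the single 2-hour infusion is the relevant comparison.

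A reader might also infer more than the documents support:

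- *A predicted fall in sodium.* One can model 5% dextrose as free water, but body water, starting sodium and the fraction retained would all be outside assumptions. With a starting sodium of 140 mmol/L and body water at 60% of weight, the modelled fall after 50 ml/kg goes from 5.6 to 10.8 mmol/L as assumed retention goes from 50% to 100%. The result mostly reflects the assumption.
- *That 15 ml/kg or one litre is a limit which the protocol accepts.* The first is a by-product of the arm (iii) dose, and the second is a hydration request. Neither is a ceiling.
- *That concentration, not time, must change.* The Background rests the high dose on peak levels ("Considering that the antifungal effect of the polyenes depends on peak concentrations"), but it gives no pharmacokinetic figure showing what a longer infusion would do to the peak.

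**Conclusion.** The concern holds as a patient-safety correction to an administration instruction. Followed as written, each 10 mg/kg infusion is 50 ml/kg of 5% dextrose at 25 ml/kg/h, and this applies to the 66 patients planned for arms (i) and (ii). The day 3 dose in arm (ii) adds a further infusion of 25 ml/kg. These figures follow from the text alone. The litre figures rest on the assumed weights, and the total with saline rests also on the saline being given.

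The size of the harm cannot be fixed from the documents. Nothing here supports a claim that the endpoints are biased, that sites will differ, or that the product instructions are breached.

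**What to change.** First, confirm whether 0.2 mg/ml is intended for the 10 and 5 mg/kg doses. Then replace the single instruction with a final concentration, maximum volume and infusion time for each of 10, 5 and 3 mg/kg, set by pharmacy within the range that the product instructions permit.

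For illustration only, bringing every infusion to the 15 ml/kg of arm (iii) would need 10/15 = about 0.67 mg/ml for 10 mg/kg and 5/15 = about 0.33 mg/ml for 5 mg/kg, with 3/15 = 0.2 mg/ml unchanged for 3 mg/kg. Slowing the infusion lowers the rate but not the volume: at 7.5 ml/kg/h, 50 ml/kg would take 50/7.5 = 6.7 hours. The choice belongs to the investigators and pharmacy.

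The cost is a protocol correction and a pharmacy memo, with no extra patients or study procedures.

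### The third limb of clinical success relies on signs that qualified the patient for entry, but eligibility requires none and the protocol does not say which baseline signs count

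*Combined protocol and SAP*

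**What the plan says.** The Primary endpoint section of the combined protocol and SAP defines clinical success at day 14 by three conditions that must all hold:

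- the highest daily temperature has stayed under 37.8 °C for 72 hours;
- there is "no increase in severity of clinical signs, symptoms, or laboratory abnormalities attributable to histoplasmosis";
- there is "resolution of at least one of the signs or symptoms of histoplasmosis that qualified the patient for study enrollment".

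The definition is attributed to reference 7.

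The Participants section admits adult "patients infected with the HIV (AIDS) who are diagnosed with DH, by the means of either" one of three test routes: urine antigen; microscopy, culture or histopathology; or PCR "in BAL samples, as well as bone marrow aspirates and tissue samples". The Exclusion criteria contain some clinical items, such as central nervous system disease and expected early death, but these only remove patients.

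Table 1 (Study activities) schedules history at baseline only. Physical examination, maximum temperature and chest X-ray are scheduled at baseline and again at day 14, where a row for determining response also appears. No row lists or records the signs or symptoms that count towards response.

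**The concern.** The third limb points back to an entry requirement that this protocol does not contain. A patient enters on a positive test, so nothing in the eligibility rules identifies the sign whose resolution is to be judged.

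This matters for three reasons. First, clinical success is the only primary outcome with stated criteria. Mycological success is also named as primary, but the protocol declines to use blood-culture or fungal clearance and makes the antigen decline secondary. Second, the trial is described as non-comparative and is sized on the precision of each arm's own rate. A scoring convention therefore shifts the reported result directly, even when it is applied alike in all arms. Third, the trial is open label at six sites and no blinded assessor is described. If the countable sign is not fixed in advance, it can be chosen at day 14 with the arm known, and sites may choose differently.

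The other two limbs give limited protection. A patient who is afebrile at entry and stays so meets the temperature limb whether or not treatment worked, and a stable patient meets the no-worsening limb. For a patient who stays afebrile and stable, the third limb decides the outcome.

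**Working it through.** **Inputs.** From Statistical analyses: expected response 88%, two-sided 90% confidence interval, half-width 10 points, 29 evaluable per arm, 10% dropout, 33 per arm, 99 in total. Assumed, because the documents give no figure: the share f of patients with no countable baseline sign, taken as 5%, 10% and 20%.

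**Step 1: the plan's own figure.** With the normal approximation, n = z² p(1−p) / d² = 1.645² × 0.88 × 0.12 / 0.10² = 28.57, rounded up to 29. At n = 29 the half-width is 1.645 × √(0.88 × 0.12 / 29) = 9.93 points. Dropout: 29 / 0.90 = 32.2, rounded up to 33; 3 × 33 = 99. The stated sample size reproduces and is not in question.

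**Step 2: the passages side by side.**

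| Question | What the protocol provides |
|---|---|
| Which sign or symptom qualifies a patient? | None; all three routes are laboratory tests |
| Do the exclusions add one? | No; they only remove patients |
| Are countable signs recorded at baseline? | History, examination and temperature are taken, but no list says which findings count |
| Are symptoms reassessed at day 14? | Examination, temperature and X-ray are repeated; history is not |
| How is a patient with no sign scored? | Not stated |

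**Step 3: what the scoring convention could do.** Let the share 1 − f respond at 88%.

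- Patients without a countable sign scored as failures: rate = 0.88 × (1 − f).
- The same patients scored as successes: rate = 0.88 × (1 − f) + f.
- The gap between the two conventions is therefore f.

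| Assumed f | Scored as failures | Scored as successes | Gap |
|---|---|---|---|
| 5% | 0.88 × 0.95 = 83.6% | 88.6% | 5 points |
| 10% | 0.88 × 0.90 = 79.2% | 89.2% | 10 points |
| 20% | 0.88 × 0.80 = 70.4% | 90.4% | 20 points |

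Precision also changes under the failure convention. With the Step 1 formula at n = 29, the half-width becomes 11.3, 12.4 and 13.9 points. The number needed for 10 points becomes 38, 45 and 57 per arm before dropout.

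**The case against.** The strongest reply is that the limb is under-specified rather than empty. Patients are admitted with disseminated disease, the tests confirm it, and baseline history, examination, temperature and X-ray will show what signs are present. Reading the limb as any sign of histoplasmosis present at enrolment is natural and workable. This stands. A reader might infer from the literal text that nobody can ever meet the limb, but the available workable reading means the documents do not support treating the endpoint as unusable. What remains is that the protocol does not adopt that reading.

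Other points also stand:

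- A reader might infer that every afebrile patient is unscorable. That is wrong: an afebrile patient with another recorded sign can be scored on the third limb, and can still fail by becoming febrile or worsening.
- A patient with no baseline sign has no symptom to pick out later. The upper figures in Step 3 therefore need a convention that counts such patients as successes, which the protocol neither states nor rules out. Retrospective choice of a sign concerns a different group, those with several baseline findings, and the table does not measure it.
- Rounding an assumed 5–20% of 33 up to 2–7 patients suggests a swing of 6–21 points. The expected gap cannot exceed the assumed share, so 5–20 points is the correct range.
- It is tempting to argue that 88% is an unfair benchmark because the trial in reference 7 had symptom-based entry. Its entry criteria cannot be checked from these documents, so nothing here rests on them.
- The protocol does not say who determines response. Knowledge of the arm is likely in an open-label trial, but it is not stated.

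The ambiguity applies to all three arms and the trial is phase II with descriptive estimates, which lowers the severity. It does not remove the problem, because each arm's own rate is the result.

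**Conclusion.** The concern holds as a gap in the primary endpoint definition. The third limb refers to qualifying signs, eligibility supplies none, and no other section says which baseline signs count or how a patient with none is scored. The consequences are a choice that can be made at day 14 with the arm known, and inconsistent scoring of patients without a baseline sign.

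The size is conditional. On the assumed shares of 5%, 10% and 20%, and 88% response in the rest, the two scoring conventions differ by 5, 10 or 20 points; at 10% the gap matches the planned half-width. If nearly all enrolled patients have signs, this numerical effect is small, though the rule would still need to be fixed. Severity: should fix, with high confidence in the gap and low confidence in its numerical effect.

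**What to change.** 1. Set a fixed list of signs and symptoms attributable to histoplasmosis, stating for each what resolution means within 14 days, and mark those present on a baseline form before randomisation.
2. Reassess the same list at day 14 and add both assessments to Table 1.
3. Reword the third limb as: *resolution by day 14 of at least one sign or symptom marked on the baseline form*.
4. Prespecify one scoring rule for patients with none marked, for example non-success in the main analysis, with a sensitivity analysis that excludes them.

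No new inclusion criterion is needed. Requiring a sign at entry would also settle the scoring, but it changes the population and is a separate decision. Reporting response in patients with a baseline temperature of at least 37.8 °C is an optional addition, since that is where the temperature limb can show improvement from baseline.

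The cost is one short form completed twice; history, examination and temperature are already scheduled at baseline, and examination and temperature at day 14. The downside is that the response rate may be slightly lower under the non-success rule.

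### Additional L-AmB courses are provided for only in arms (i) and (ii), so comparing the additional-course endpoint with arm (iii) is likely to be biased in that arm's favour

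*Combined protocol and SAP*

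**What the plan says.** The Secondary endpoints section lists, for the trial as a whole: "Secondary endpoint will also include need for an additional antifungal course with L-AmB, during 24 weeks of follow up". It does not restrict the endpoint to particular arms or say what counts as need. Table 1 carries a matching row, also without an arm restriction.

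The Rescue therapy section lets the physician give further L-AmB at 3 mg/kg "in case the attendant physician suspect of absence of response with the induction regimen", and restricts the provision, which is to "apply for failing patients receiving a single 10 mg/kg of L-AmB; or 10 mg/kg on day 1, followed by 5 mg/kg on day 3". Those are arms (i) and (ii). The supply estimate follows the same line: it takes a 12% failure rate from an earlier trial of L-AmB at 3 mg/kg and applies it to two arms ("Considering that 66 patients will be evaluated in arms (i) and (ii) of the study (high-doses of L-AmB"), which gives 8 courses. Arm (iii) is not mentioned.

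Under Intervention, arm (iii) receives L-AmB at 3 mg/kg for 2 weeks, so its scheduled treatment runs to about day 14.

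On analysis, the Trial design section calls the trial non-comparative, but the Objectives include comparing the regimens. The Statistical analyses section plans exploratory comparisons and says: "Categorical variables will be compared with Fisher exact test or chi-square test, as appropriate". It gives no significance level.

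**The concern.** The endpoint is meant to show how often the assigned induction was not enough. In arms (i) and (ii) a failing patient has a defined route to an additional course. In arm (iii) the plan describes no such route. Until day 14 a failing patient there is still receiving scheduled L-AmB at the dose stated for rescue, so nothing additional is naturally recorded. After day 14 the documents neither provide a further course nor say how a failure is scored. The recorded event therefore depends partly on the randomised arm and not only on the outcome.

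If the three proportions are set side by side or tested, equal efficacy can look like a disadvantage of the short regimens. The Research Justification section says the results may support a phase III trial, so a misleading contrast on this endpoint could colour that decision.

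**Working it through.** **Inputs.** Failure rate 12% (Rescue therapy; the complement of the 88% response in Statistical analyses, where equal response in all arms is expected). 33 randomised and 29 evaluable per arm (Statistical analyses). Assumed here: a two-sided 5% level, and the share q of arm (iii) failures that are recorded as an additional course.

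**The plan's own figures.**
- Rescue courses: 0.12 × 66 = 7.92, rounded to 8. Reproduced.
- Sample size: 1.645² × 0.88 × 0.12 / 0.10² = 28.57, rounded up to 29; 29 / 0.90 = 32.2, rounded up to 33; 3 × 33 = 99. Reproduced, and not affected by this point.
- The same rate in arm (iii) gives 0.12 × 33 = 3.96, about 4 failures, for which no additional course is foreseen.

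**Model.** Let X be the courses recorded in the short-course group, X ~ Bin(m, 0.12), with m = 33 for one arm or 66 for arms (i) and (ii) pooled. Let Y be those in arm (iii), Y ~ Bin(33, 0.12q). The rejection rate is the sum of P(X = x) P(Y = y) over all tables with Fisher p ≤ 0.05. True failure is 12% in every arm, so any excess of rejections over the even-recording row comes from recording.

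**None recorded in arm (iii) (q = 0).**
- One arm against arm (iii): 5/33 v 0/33 gives p = 2 × C(33,5)/C(66,5) = 0.053; 6/33 v 0/33 gives p = 2 × C(33,6)/C(66,6) = 0.024. So X ≥ 6 is needed, and P(X ≥ 6) = 0.198.
- Pooled: 7/66 v 0/33 gives p = 0.09 and 8/66 v 0/33 gives p = 0.049. So X ≥ 8 is needed, and P(X ≥ 8) = 0.544.
- With 29 per arm: 0.127 for one arm and 0.395 pooled.

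**By recorded rate in arm (iii), 33 per arm.** Each cell gives one short-course arm v arm (iii) / pooled v arm (iii).

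| Recorded rate in arm (iii) | Fisher p ≤ 0.05 | Arm (iii) shows the lower proportion |
|---|---|---|
| 0% (q = 0) | 20% / 54% | 98.5% / >99.9% |
| 3% (q = 0.25) | 9% / 22% | 89% / 95% |
| 6% (q = 0.5) | 4% / 9% | 74% / 82% |
| 12% (q = 1, even recording) | 1.5% / 3.2% | 42% / 47% |

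The direction is the same whenever arm (iii) failures are under-recorded relative to the other arms. The size falls quickly as recording improves.

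**The case against.** A reader might infer that arm (iii) must score near zero by protocol. The documents do not say so. The endpoint is worded as need, not as receipt under the rescue provision. The Table 1 row applies to every patient, and nothing forbids L-AmB in arm (iii) after its 2 weeks or bars its recording. What the text shows is silence on arm (iii), from which under-recording is likely but not certain.

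A reader might also take this endpoint as the main evidence on whether short induction suffices, so that arm (iii) would look better whatever the efficacy. That goes too far. Day-14 clinical success has one definition for all arms, and mortality and survival are defined alike for all arms. An excess of failures in arm (iii) could show on those.

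The 54% should not be the headline. It needs a pooled contrast that the plan never specifies, a 5% level that it does not state, no dropout, and no event in arm (iii). The p = 0.049 is fragile: one course fewer, 7/66 v 0/33, gives 0.09, and one event in arm (iii), 8/66 v 1/33, gives 0.26.

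Finally, the trial is labelled non-comparative, and the sentence on exploratory comparisons speaks of subgroups, not arms. That weakens the claim that this test will be run. It does not remove the point: the Objectives say the regimens will be compared, and unequal recording distorts side-by-side proportions even without a test.

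**Conclusion.** The point holds in a limited form. The endpoint covers all arms and the provision behind it covers two, so any comparison with arm (iii) is likely to be biased in that arm's favour. Arm (i) against arm (ii) is not affected by this asymmetry.

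At 12% true failure in every arm and a 5% two-sided Fisher test, the false-signal rate for one short-course arm against arm (iii) is at most 20% (13% with 29 per arm), reached when no arm (iii) failure is recorded. It is 9% with 3% recorded and 4% with 6% recorded, against 1.5% under even recording. The pooled figures are 54% (39% with 29 per arm), 22%, 9% and 3%. The recorded rate in arm (iii) is an assumption; the documents give no basis for choosing one value.

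This is a minor-to-moderate matter. It concerns one exploratory secondary endpoint and leaves the sample size and the primary outcome untouched.

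**What to change.** - Reconcile the Secondary endpoints and Rescue therapy sections, so that it is clear which arms the endpoint describes and what counts as need.
- Report additional L-AmB courses as a descriptive proportion with a confidence interval. Compare at most arm (i) with arm (ii), and state that the endpoint is neither tested against arm (iii) nor interpreted relative to it.
- Base any cross-arm comparison of induction failure on the day-14 clinical response definition, which already applies to all arms.
- Record any L-AmB given beyond the assigned regimen in every arm, including in arm (iii) past its planned 2 weeks.

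A new composite that adds physician-suspected non-response is not needed. In an open-label trial the threshold for suspicion may differ between patients who have finished L-AmB by day 1 or day 3 and those still receiving it, and before day 14 arm (iii) has not completed its induction.

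The cost is a wording change, recording of extra L-AmB in all arms, and one fewer exploratory comparison across arms. No extra patients or visits are needed, and no change to who may receive rescue is proposed.
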